SLE is a chronic inflammatory disease that has renal effect in about half of patients. Lupus nephritis is a major risk factor for morbidity and mortality in patients with SLE, and in spite of strong anti-inflammatory and immunosuppressive therapies still ends in CKD or ESRD. (5)

Based on this observation, we aim to determine the effect of SGLT2i treatment in patients with glomerulonephritis secondary to SLE who either is diabetic or non-diabetic.

Aim of the work

This study aims to assess SGT2i role in regression of ongoing kidney and cardiac diseases among lupus nephritis patient either diabetic or non-diabetic under different immunosuppressive therapy.

Patients and methods

Technical design:

Study sitting: .1

Nephrology and renal transplant unit at urology and nephrology center in Mansoura University.

It will include 100 patients with lupus nephritis, Diagnosis of glomerulonephritis was performed by renal biopsy, and all of the renal biopsies were carried out at urology and nephrology center.

Patients with an estimated glomerular filtration rate (eGFR) >30 ml/min/1.73m2 will be randomized into two groups

- Study group will receive SGLT2i inhibitor as add on drug or replace
 another drug according to patient clinical situation, Dapagliflozin 10
 mg and 25 mg will be used once daily with or without food.
 - Control group will be maintained on placebo. •

The primary endpoint will be sustained decline in eGFR ≥50%, ESKD, or kidney or cardiovascular death

We will follow up all patients for 12 months and compare their results.

2. Inclusion criteria:

- Patients aged more than 16 year. .1
- Willing to sign informed consent. .2
- Diagnosis of SLE according to EULAR/ACR classification .3 criteria.
 - Renal biopsy showed lupus nephritis. .4
- Patient with eGFR > 30 ml/min/1.73m2 by cockcroft-gault .5 equation.

3. Exclusion criteria:

- Patients with eGFR <30 ml/min per 1.73 m2. .1
 - Current pregnancy or lactation. .2
- Medical history of chronic disease (CLD, cancer, severe .3 respiratory distress, gastrointestinal tract lesions).
- Patients refusing to participate in the study or lost follow up. .4
- Evidence of urinary obstruction of difficulty in voiding at .5 screening.

- Patients who are receiving high dose diuretics or combined .6 ACEI, ARBS.
- Patients who have frequent hypotensive episode or SBP .7 <100 mmHg.

Operational design:

Study Protocol:

Patients included in the study will treated with dapaglifilozin

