 initiated at a total daily dosage of 10 mg/kg per day.

Study design:

Type of the study: randomized controlled study.

The following data will be gathered and evaluated for all patients:

I-before intervention:

- Serum creatinine, Creatinine clearance. .1
- 24 hour urine protein, urine protein/creatinine ratio. .2
 - Urine analysis. .3
 - HBA1c. .4
 - HGB. .5
 - Uric acid and lipid profile. .6
 - Lupus serology. .7

II-after intervention: All patients will be evaluated monthly regarding:

- Serum creatinine, creatinine clearance. .1
- 24 hour proteinuria, protein/creatinine ratio. .2
- Fasting, random and postprandial glucose levels. .3
 - CNI trough level if used. .4
 - Urine analysis. .5
 - HGB level. .6
 - Uric acid, lipid profile. .7
 - Lupus serology. .8

Cardiovascular assessment: .9

ECCHO.

Atherosclerosis and vascular calcification incidence (NCCT model).

Regular measurement of blood pressure each visit.

Outcomes:

- Effect of dapagliflozin compared to placebo on eGFR. .1
- Effect of dapagliflozin compared to placebo on systolic/diastolic blood .2 pressure.
 - Effect of dapagliflozin compared to placebo on body weight. .3
- Safety of dapagliflozin vs. placebo the number of hypoglycemia .4 episodes between groups and serious adverse events.

Statistical Analysis:

Qualitative data were displayed in cross tabulations, and quantitative data were described in terms of arithmetic mean ± SD. Bivariate techniques were used for initial evaluation of contrasts. Thus, the chi-square and Fisher's exact tests were used for comparisons of frequencies of qualitative variables; the Mann-Whitney test and the unpaired t-test were used for comparisons of means of two quantitative variables. A p-value <0.05 was considered significant. Graft and patient survival rates were assessed using the Kaplan-Meier method. All analyses were carried out using the computer package SPSS for windows, release 16 SPSS Inc. Chicago, III, USA.

Administrative design •

Informed consent will be obtained from all subjects and the approval will be obtained from institutional review board (IRB) in Faculty of Medicine, Mansoura University. There is no funding.

Research question

The main research question is: Does use of SGLT2i will show superiority over conventional lines of treatment of lupus nephritis patient as regard efficacy and safety.

Rationale and justification

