Statistical Analysis Plan

Document Control

Title: Statistical Analysis Plan for the Study of SGLT2 Inhibitors in Lupus Nephritis Patients

Protocol ID: [NCT05748925] Version: 1.0 Date: [11/3/2024] Principal Investigator: [[name]] Statistician: [[name]] Approval Signatures: Principal Investigator: [name] Statistician: [name]

Table of Contents

- 1. Introduction
- 2. Study Design
- 3. Study Objectives
- 4. Endpoints
- 5. Sample Size Justification
- 6. Statistical Methods
- 7. Handling of Missing Data
- 8. Interim Analysis
- 9. Safety Analysis
- 10. Data Quality and Management
- 11. Software
- 12. Appendices

1. Introduction

• **Purpose of the SAP**: This document outlines the statistical approach for analyzing data from the clinical trial studying the effects of SGLT2 inhibitors on renal, cardiovascular, and hematological outcomes in lupus nephritis patients.

2. Study Design

Design: Randomized, double-blind, placebo-controlled clinical trial.

Study Duration: Conducted from September 2022 to November 2023

Randomization: Patients were randomly assigned to either dapagliflozin (10 mg once daily) or placebo groups using computer-generated random tables in a 1:1 ratio stratified by age and gender.

Blinding: The study was double-blinded, and all trial staff and participants remained unaware of individual treatment assignments until study completion.

3. Study Objectives

Primary Objective: To evaluate the impact of SGLT2 inhibitors on renal, cardiovascular, and hematological parameters in lupus nephritis patients.

Secondary Objective: To explore changes in body weight, BMI, and other echocardiographic and iron profile parameters over 12 months.

4. Endpoints

Primary Endpoints

Renal Function: Serum creatinine, eGFR, and 24-hour urine protein

Cardiovascular Health: BNP levels and coronary calcification via NCCT

Hematological Parameters: Hemoglobin and erythropoietin levels

Hepcidin Level: Measured before and after intervention

Secondary Endpoints

Body Weight and BMI: Assessed at baseline and follow-up visits.

Echocardiographic Findings: Assessed pre- and post-intervention.

Iron Profile: Serum ferritin and TSAT

5. Sample Size Justification

Calculation: A sample size of 100 patients was targeted, accounting for potential dropouts, to provide sufficient power (80%) at a significance level of 0.05 to detect differences between the two groups.

6. Statistical Methods

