
General Considerations

Significance Level: A two-sided alpha level of 0.05 will be used for all primary analyses.

Analysis Populations:

Intent-to-Treat (ITT): All randomized patients will be analyzed according to their assigned group.

Per-Protocol (PP): Only patients completing the study without major protocol violations.

Primary Endpoint Analysis

Renal Outcomes: ANOVA for repeated measures for serum creatinine and eGFR if normally distributed, and the Friedman test for non-normally distributed data. Post-hoc tests using Bonferroni correction.

Cardiovascular Outcomes: Mann-Whitney U test for BNP levels and coronary calcification between groups.

Hematological Outcomes: Paired t-test for hemoglobin and erythropoietin levels if data is normally distributed; otherwise, Wilcoxon signed-rank test.

Secondary Endpoint Analysis

Body Weight and BMI: Compared over time using ANOVA for repeated measures.

Echocardiographic Parameters: Analyzed with paired t-tests, adjusted with Bonferroni correction.

Iron Profile: Analyzed pre- and post-intervention using ANOVA or Kruskal-Wallis for non-normally distributed variables.

Categorical Variables

Chi-Square Test: For between-group comparisons of categorical data (e.g., presence of diabetes, hypertension).

7. Handling of Missing Data

Imputation: Last observation carried forward (LOCF) for data missing at random; multiple imputation for extensive missing data.

Sensitivity Analysis: Conducted to evaluate the robustness of primary endpoint findings against different missing data assumptions.

8. Interim Analysis

Timing: An interim analysis is planned at the halfway point (6 months).

Stopping Rules: An O'Brien-Fleming approach will be applied to adjust the significance threshold for interim testing, allowing for an earlier stop for efficacy or safety concerns.

9. Safety Analysis

Adverse Events (AEs): Summarized by type, frequency, and severity. Fisher's exact test will be used to compare AE rates between groups.

Specific Safety Parameters: Monitoring for hypotension, electrolyte imbalances, and kidney function.

10. Data Quality and Management

Data Quality Measures: Includes data verification, regular audits, and query resolution.

Database Lock: Data will be locked and verified prior to the final analysis.

11. Software

Statistical Software: All analyses will be conducted using SPSS (Version 25).

12. Appendices

	Control group. (n= 41)	Study group. (n= 38)	P value

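### The protocol's treatment instruction gives dapagliflozin as 10 mg/kg per day and its study-group text adds 25 mg with no rule; the SAP reports only 10 mg once daily

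*Protocol*

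**What the plan says.** The two documents contain three statements of the dapagliflozin dose.

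- **Protocol, Technical design, study group.** Two fixed strengths are named, 10 mg and 25 mg: "mg and 25 mg will be used once daily with or without food". The control arm is described separately: "Control group will be maintained on placebo".
- **Protocol, Operational design, Study Protocol.** The sentence opens "Patients included in the study will treated with dapaglifilozin" and continues "initiated at a total daily dosage of 10 mg/kg per day". It is weight-based and is not limited to one arm.
- **SAP section 2, Randomization.** One fixed dose: "Patients were randomly assigned to either dapagliflozin (10 mg once daily) or placebo groups".

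Neither document reconciles these statements, and no amendment log is present. SAP section 2 gives the study period as "Conducted from September 2022 to November 2023", and the SAP's Document Control block reads "Version: 1.0 Date: [11/3/2024".

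**The concern.** The mg/kg figure sits in the instruction that tells staff what to give, not in background text. Followed literally, it would give a dose far above either fixed strength in the same protocol. The sentence also covers every included patient, although the control arm is on placebo.

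The 25 mg strength is a separate problem. The protocol does not say whether 25 mg is a titration step, an alternative at the clinician's choice, or a leftover. The nearby reference to the patient's clinical situation concerns whether dapagliflozin is added or replaces another drug. Stretched to cover dose, it would still not be a rule. The word for starting treatment in the operational sentence could mean that a later increase was intended, but then the titration rule is missing.

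What is at stake is a clear statement of the experimental treatment. A reader of the efficacy comparison (SAP Table 6) and the side-effect comparison (SAP Table 10) needs to know whether one dose or a mixture of two was compared with placebo. The protocol and the SAP answer differently.

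**Working it through.** No sample-size or power formula applies. The check is a unit conversion and a side-by-side comparison.

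**Inputs**

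- Operational dose: 10 mg/kg per day (Protocol, Operational design).
- Study-group doses: 10 mg and 25 mg once daily (Protocol, Technical design).
- SAP dose: 10 mg once daily (SAP section 2).
- Baseline weight: study group 90 ± 15 kg, control group 78.9 ± 14 kg (SAP Table 1).

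**Step 1: the operational dose read literally.** Daily dose in mg = 10 × weight in kg.

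| Weight | Literal dose | Multiple of 10 mg | Multiple of 25 mg |
|---|---|---|---|
| 75 kg (study mean − 1 SD) | 750 mg/day | 75 | 30 |
| 90 kg (study mean) | 900 mg/day | 90 | 36 |
| 105 kg (study mean + 1 SD) | 1050 mg/day | 105 | 42 |

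The control mean of 78.9 kg is included because the sentence covers all patients; it gives 789 mg/day. The literal dose fits neither fixed strength.

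**Step 2: is a unit slip the better reading?** The number 10 appears as a fixed mg dose in the study-group text and again in the SAP. At 90 kg, 10 mg is 10/90 = 0.11 mg/kg, so the weight-based reading cannot be a restatement of the same dose. Removing the per-kg unit brings the operational sentence into line with the SAP and with the lower strength in the study-group text. This is an inference, but the documents support it.

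**Step 3: what remains once the unit is corrected.**

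| Statement | Dose after correction | Agrees with SAP? |
|---|---|---|
| Operational section | 10 mg per day | Yes |
| Study-group text, lower strength | 10 mg once daily | Yes |
| Study-group text, upper strength | 25 mg once daily | No: 25/10 = 2.5-fold |

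So only the mg/kg unit and the 25 mg strength conflict with the SAP.

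**Step 4: the order of the documents.** The SAP date can be read two ways. Counted from 30 November 2023, 11 March 2024 is 102 days later and 3 November 2024 is 339 days later. Either way the SAP follows the stated conduct period. Its 10 mg is a description after the event, which carries weight for what was given but does not amend the protocol.

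**Step 5: how many patients the dose statement must cover.** The target was 100, and the SAP tables cover 41 + 38 = 79. The number randomised to the active arm is not given in the text. The flow chart (SAP Figure 1) could not be read here, so it was not possible to check whether it states that number or the allocated dose.

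**The case against.** The strongest reply is that this is an obvious slip in a finished trial. The SAP names one regimen in the past tense, correcting the protocol changes no patient's treatment, and no result is said to move. On that view it is a documentation note.

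Much of this stands. The 900 mg figure measures the written error and says nothing about actual dosing. The study-group text is not wrong as a whole, since its 10 mg agrees with the SAP. But a unit slip does not explain the 25 mg strength, and a later SAP does not correct a treatment instruction in the protocol.

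A reader might infer that the Per-Protocol analysis collapses, because every study-arm patient given 10 mg would breach the literal 10 mg/kg instruction. The documents do not support that. SAP section 6 defines the set as "Only patients completing the study without major protocol violations" and does not say what a major violation is or that dose counts. No table in the SAP appendices is labelled Per-Protocol. Counting violators against a figure already recognised as a slip is not realistic. The undefined term is a separate gap that would remain if the dose text were perfect.

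A reader might also infer that some patients took 25 mg or a weight-based dose. No statement or table in the documents shows this.

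**Conclusion.** The point holds as an uncorrected inconsistency in the dose of the investigational drug, and it should be fixed. The operational instruction is wrong as written: about 900 mg/day at 90 kg against 10 mg in the SAP, and not limited to the active arm. With the unit corrected, what remains is an unexplained 25 mg strength, 2.5 times the SAP dose, in an unknown number of patients that may be zero.

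This rests on reading mg/kg as a slip for mg, which is an inference, and on taking the SAP's 10 mg once daily as the reported regimen. It makes no claim about harm, actual dosing or any reported result. The 38 study-arm patients in the tables cannot be assumed to be everyone randomised to that arm, so a confirmation limited to them could leave some out.

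**What to change.** 1. Issue a dated erratum or clarification to the protocol, keeping the existing text visible. Change the operational dose to: *dapagliflozin 10 mg once daily in the active arm; placebo in the control arm*.
2. In the same document, either withdraw the 25 mg strength or state who received it and under what rule. Deleting it silently would hide what was planned.
3. In the report, state the dose actually given to every patient randomised to the active arm, not only the 38 tabulated, and list any 25 mg exceptions. Neither document mentions dispensing or treatment records. If they do not allow this statement, the report should say so.
4. If a Per-Protocol analysis uses dose as a criterion, take 10 mg once daily as the standard and label the choice post hoc, because the SAP already contains 12-month outcome tables.

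The cost is a short erratum, a sentence or two in the report and, where item 4 applies, one labelled clause in the SAP. No new data are needed, and no reanalysis is called for unless exceptions emerge.

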End diastolic volume; Chi square test; Student t- test; Man, Whitney test; Level of significance < 0.05.

Table (10): Comparison between both groups as regard post intervention side effects

	Control group. (n= 41)	Study group. (n=38)	P value
AKI episodes No. (%)			
- No	38 (92.7%)	31 (81.6%) 5 (13.2%)	0.17
- once	1 (2.4%) 2 (4.9%)	2 (5.3%)	
- twice			
UTI No. (%)			
- No	35 (85.4%) 4 (9.8%)	31 (81.6%) 5 (13.2%)	0.8
- once	2 (4.9%)	2 (5.3%)	
- more than once			
Gynecological infection No. (%)	1 (2.4%)	2 (5.3%)	0.6
Viral infection No. (%)	1(2.4%)	1 (2.6%)	1
MMF intolerance No. (%)	1 (2.5%)	2 (5.3%)	0.6
Renal biopsy No. (%)	2 (4.9%)	1 (2.6%)	0.6
Increase steroid dose No. (%)	7 (17.1%)	4 (10.5%)	1

UTI: urinary tract infection episodes; AKI: acute kidney injury; chi-square test for categorical data. Categorical data are expressed as number (percentage).; Level of significance < 0.05.

figure1: flow chart of participating populations

Figure (2) shows difference between individual which had improved eGFR or not as regard to their basal eGFR in total cohort, which found that improving eGFR had been occurred in patients with lower eGFR (107±50 vs 137±58 ml/min/m²

Figure (3) show no significant difference between the drug and placebo groups (p=0.857). as regard incidence of anemia before intervention, the drug group has 23 anemic participants (60.5%) versus 24 participants (58.5%) in the placebo group, while post intervention, In the anemia category, the drug group has 16 participants (42.1%), while the placebo group has 22 participants (53.7%) with non-significant differences (p = 0.3)

Figure (4) differences in body weight between both groups at different time points:

Glossary of Terms and Abbreviations

AA	Amino Acids
ABIN	A20 Binding Inhibitor Of NF-Kb
ACE	Angiotensin-Converting Enzyme Inhibitors
ACR	American College of Rheumatology
AKI	Acute Kidney Injury
ALCAM	Activated Leucocyte Adhesion Molecule
ALP	Alkaline Phosphatase
AMP	Adenosine Monophosphate
АМРК	Amp-Activated Protein Kinase
ANA	Antinuclear Antibodies
ANG II	Angiotensin 2
ANOVA	Analysis Of Variance
ANTI-DSDNA	Anti Double Stranded Deoxyribonucleic Acid
	Antibodies
ANTI-SM	Anti-Smith Antibodies
APLS	Antiphospholipid Syndrome
ARBS	Angiotensin 2 Receptor Blockers
ATN	Acute Tubular Necrosis
ATP	Adenosine Triphosphate
BAFF	B-Cell-Activating Factor
BLISS	B Lymphocyte Stimulator Inhibitor Belimumab
	Plus Standard Therapy
BMI	Body Mass Index
BNP	Brain Natriuretic Peptide
BP	Blood Pressure

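### The SAP omits three outcomes the protocol lists (blood pressure, hypoglycaemia episodes, serious adverse events) from its endpoints, methods and tables without explanation

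*Protocol*

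**What the plan says.** The protocol's Outcomes list has four numbered entries: eGFR, blood pressure, body weight and safety. The blood pressure entry is "Effect of dapagliflozin compared to placebo on systolic/diastolic blood" pressure. The safety entry begins "Safety of dapagliflozin vs. placebo the number of hypoglycemia" and continues "episodes between groups and serious adverse events". The data to be gathered after intervention include "Fasting, random and postprandial glucose levels" (monthly) and, under cardiovascular assessment, "Regular measurement of blood pressure each visit". The research question asks about superiority over conventional treatment in "lupus nephritis patient as regard efficacy and safety".

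SAP section 4 keeps eGFR as a primary and body weight as a secondary endpoint. Blood pressure, hypoglycaemia and serious adverse events are not listed there, and section 6 gives no analysis for them. SAP section 9 plans a summary of adverse events by type, frequency and severity, with Fisher's exact test between groups. It also names "Monitoring for hypotension, electrolyte imbalances, and kidney function". The results table for safety is Table 10, titled "Comparison between both groups as regard post intervention side effects".

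**The concern.** A reader who follows the SAP alone would not compare blood pressure between arms and would have no instruction to count hypoglycaemia episodes or serious adverse events. The protocol named all three. Blood pressure is an outcome in its own right. The other two are the only components of the protocol's safety outcome.

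Timing adds to the concern. SAP version 1.0 carries a 2024 date, gives a study period ending in November 2023, and has outcome tables in its appendix. When outcomes disappear from a plan finalised with results in hand, and no reason is recorded, a reader cannot tell whether they were uninformative, uncollected or unfavourable.

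The outcomes also matter in this population. Tables 1 and 2 show 75 of 79 patients with hypertension (37 + 38), 18 with diabetes (7 + 11) and 53 on ACE inhibitors or ARBs (26 + 27). The protocol excludes patients with frequent hypotension or a systolic pressure below 100 mmHg, so it treated low blood pressure as a concern.

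**Working it through.** This is mainly a comparison of the documents. The SAP's target of 100 patients cannot be reproduced, because no effect size, standard deviation, event rate or dropout rate is given, and it is not tied to any of these outcomes.

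**1. Each outcome, traced through the documents**

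| Protocol outcome | SAP 4 | SAP 6 | SAP 9 | SAP tables |
|---|---|---|---|---|
| eGFR | primary | yes | kidney function named | Table 6, by arm and visit |
| Blood pressure | absent | absent | hypotension only | none |
| Body weight | secondary | yes | – | baseline in Table 1; Figure 4 caption |
| Hypoglycaemia episodes | absent | absent | not named | none |
| Serious adverse events | absent | absent | not named; severity only | none |

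**2. SAP section 9 against Table 10.** The rows of Table 10 are AKI, UTI, gynaecological infection, viral infection, MMF intolerance, renal biopsy and increased steroid dose. Of the three parameters that section 9 names, kidney function is covered (AKI in Table 10, creatinine and eGFR in Table 6). Hypotension and electrolytes are not. Sodium, potassium and random blood sugar appear only in the baseline laboratory table.

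**3. Severity is not seriousness.** Severity grades intensity, while seriousness depends on the consequence of the event. A summary by severity therefore does not yield a count of serious adverse events, and Table 10 shows no severity grading either.

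**4. What the protocol schedules**
- Blood pressure: each visit. It is missing from the pre-intervention list. The exclusion for low systolic pressure implies a screening systolic reading, but nothing specifies a baseline diastolic one.
- Hypoglycaemia: monthly glucose values are scheduled, but no episode is defined and no method is given for capturing episodes between visits.
- Serious adverse events: no collection procedure is described.
- Electrolytes: not on the monthly list.

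**5. What the tabulated numbers can support (41 control, 38 study)**
- *Continuous outcome such as blood pressure.* Detectable difference at 80% power, two-sided 0.05, normal approximation: (1.960 + 0.842) × √(1/41 + 1/38) = 2.802 × 0.2252 = 0.63 SD. At 50 per arm it is 2.802 × √(2/50) = 0.56 SD.
- *Zero events.* One-sided 95% upper bound = 1 − 0.05^(1/n). For n = 38 this is 7.6%; for n = 41 it is 7.0%.
- *Power of Fisher's exact test at 41 vs 38.* The event rates are assumed, as the documents give none:

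| Assumed rates | Power |
|---|---|
| 5% vs 15% | 26% |
| 5% vs 20% | 48% |
| 5% vs 25% | 70% |
| 5% vs 30% | 85% |

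Blood pressure can carry a between-arm comparison of moderate precision. The event outcomes are mainly descriptive.

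**The case against.** The best defence is that safety outcomes normally sit in a safety section, and SAP section 9 has one. It plans a between-arm comparison of all adverse events, under which hypoglycaemia and serious events could be captured as event types, and it names hypotension. The protocol's own statistical section also offers general two-group tests that would fit blood pressure. This stands in part: a reader might infer that the trial cannot answer its safety question at all, and the documents do not support that. AKI, infections and MMF intolerance are compared by arm. What remains is that the three outcomes are not named, the general plan guarantees neither an episode count nor a tabulation of serious events, and Table 10 does not deliver everything section 9 names.

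Three other inferences are tempting and also go too far.
- *That selective reporting has occurred.* The documents show an unexplained omission in a SAP dated after the study. They show neither motive nor the missing results, and the tables are a SAP appendix rather than a final report.
- *That half of the protocol's outcomes were dropped.* Only blood pressure has no SAP analysis of any kind, and the numbered list is not the whole set: the protocol separately states a composite primary endpoint.
- *That the repair needs no new data.* As step 4 of the working shows, this is unsafe for hypoglycaemia episodes, serious events, on-study electrolytes and baseline diastolic pressure. Printing zeros by default could present uncollected data as absence of events.

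**Conclusion.** The point holds as a gap in specification and reporting that should be corrected. Three protocol-listed outcomes are missing from the SAP's endpoints, methods and tables without a stated reason, and two of the three safety parameters that SAP section 9 names have no on-study results. The safety answer is incomplete rather than impossible, and selective reporting is a concern rather than a finding.

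The conclusion assumes that the visible endpoint list and Tables 1 to 10 are complete. The figures themselves could not be seen, but none of their captions mentions these outcomes. Restoring the event outcomes would not give a confirmatory safety comparison at 41 vs 38. Its value lies in showing the counts and their uncertainty.

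**What to change.** 1. **SAP section 4 and section 6:** add systolic and diastolic blood pressure as secondary endpoints, compared between arms at 12 months in the ITT set and adjusted for baseline blood pressure where a baseline reading exists. State how the 79 tabulated patients relate to all those randomised.
2. **SAP section 9 and Table 10:** add, by arm, patients with at least one hypoglycaemia episode and the number of episodes, patients with at least one serious adverse event, hypotension, and electrolyte abnormality. State the definition used for each. Give the risk difference with a 95% confidence interval for the patient-level rows, and describe these comparisons as mainly descriptive.
3. **Zeros:** print zero only where the item was collected and none occurred; otherwise write that it was not collected.
4. **Labelling:** mark these as protocol-specified outcomes restored to the SAP after study completion, or record why any was removed.

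The cost is a few SAP lines and table rows. Blood pressure was scheduled at each visit and glucose monthly; the remaining rows depend on what was recorded.

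### The protocol's declared safety outcome, hypoglycemia episodes and serious adverse events, is neither named in SAP 9 nor reported in Table 10

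*Protocol*

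**What the plan says.** The protocol lists four outcomes. The fourth is safety, and its text runs across two lines: "Safety of dapagliflozin vs. placebo the number of hypoglycemia" and then "episodes between groups and serious adverse events". The protocol's post-intervention schedule also has a monthly item, "Fasting, random and postprandial glucose levels".

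SAP section 9 has two bullets. The general one says adverse events are "Summarized by type, frequency, and severity. Fisher's exact test will be used to compare AE rates between groups". The specific one reads "Monitoring for hypotension, electrolyte imbalances, and kidney function".

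Table 10 in the SAP appendix is titled "Comparison between both groups as regard post intervention side effects". Its rows are AKI episodes, UTI, gynecological infection, viral infection, MMF intolerance, renal biopsy and increased steroid dose. Its footnote reads "UTI: urinary tract infection episodes; AKI: acute kidney injury; chi-square test for categorical data".

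**The concern.** Safety is part of the protocol's main research question and of its objectives, and item 4 is the one place where the protocol says what will be compared. If the SAP does not carry that outcome forward and the results table has no row for it, following the plan as written leaves the stated safety question unanswered.

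This matters for a glucose-lowering drug given to a mixed population. In Table 1, 11 of 38 study patients and 7 of 41 controls had diabetes. It also matters for seriousness. Table 10 shows AKI in 5 + 2 = 7 of 38 study patients and 1 + 2 = 3 of 41 controls, and nothing tells a reader whether any of these events was serious. SAP section 8 allows early stopping for safety reasons, yet the protocol's own safety outcome does not appear in the document that would govern that decision.

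**Working it through.** The point is a comparison of texts. The plan gives no figure for safety that could be reproduced.

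**1. The three lists side by side**

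| Item | Protocol Outcomes, item 4 | SAP 9 | SAP Table 10 |
|---|---|---|---|
| Hypoglycemia episodes | named | not named | no row |
| Serious adverse events | named | not named (severity only) | no row |
| Hypotension | not named | named | no row |
| Electrolyte imbalance | not named | named | no row |
| Kidney function | not named | named | AKI episodes |
| Three infection rows, MMF intolerance, renal biopsy, steroid increase | not named | not named | reported |

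Of the two declared components, SAP 9 names 0 and Table 10 reports 0. Of SAP 9's three specific parameters, Table 10 carries 1. No two of the three lists match.

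**2. Whether another table fills the gap**

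Random blood sugar, sodium and potassium appear in the baseline laboratory table only. Tables 6 to 9, which hold the follow-up results, contain no glucose, electrolyte, hypoglycemia or serious-event data.

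**3. Whether the general adverse-event rule is enough**

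- *Definition.* Neither document defines a hypoglycemia episode. The lowest baseline random blood sugar was 66 mg/dL in controls and 64 mg/dL in the study group. Whether a low reading at a monthly visit counts as an episode depends on a rule that is not written down.
- *Seriousness.* A severity grade does not identify serious events, and neither document defines a serious adverse event.
- *Measure.* The protocol counts episodes, which can recur in one patient. Fisher's exact test applies to a table of patients. It does not compare numbers of episodes per patient.
- *Application.* SAP 9 names Fisher's test, while Table 10's footnote names chi-square only. Recomputing the two-by-two rows shows a mixture. Gynecological infection and MMF intolerance (1/41 v 2/38) give Fisher 0.61 and uncorrected chi-square 0.51, with 0.6 printed. Renal biopsy (2/41 v 1/38) gives Fisher 1.0 and uncorrected chi-square 0.60, also with 0.6 printed. Increased steroid dose (7/41 v 4/38) gives Fisher 0.52, uncorrected chi-square 0.40 and Yates-corrected 0.61, with 1 printed. So one cannot assume that Table 10 is simply SAP 9's rule carried out.

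**4. Context only: what a printed zero would mean**

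The exact two-sided 95% upper limit for 0 events in n patients is 1 − 0.025^(1/n). It is 9.3% for n = 38, 8.6% for n = 41 and 28.5% for the 11 study patients with diabetes. These limits reflect sample size and would be the same if Table 10 printed zeros. They do not measure the defect.

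**The case against.** The best defence is that SAP 9's general bullet covers every adverse event by type, with a between-group test. Hypoglycemia recorded as an adverse event would fall under it, and the hypotension line sits beside that bullet without claiming to replace the protocol's outcome. This stands. A reader might infer that the declared comparison cannot be made, or that safety has been redefined. The documents show only that the comparison is not named and not reported.

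The defence on episode counts also has some force. SAP 9 speaks of adverse-event rates without saying they are yes/no per patient. Table 10 splits AKI and UTI by recurrence. The protocol's statistics section provides the Mann-Whitney test for quantitative variables, which could be applied to episodes per patient. The tools therefore exist, but neither document assigns them to this outcome.

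Three further inferences are not supported:

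- *Deaths went unreported.* Table 10 has no death row, but the content of the participant flow chart (Figure 1) is not visible in the text available for review and may show them. Item 4 does not list deaths separately either.
- *The missing rows are offered as evidence of safety.* No passage draws a conclusion on hypoglycemia.
- *The data are certainly on file.* Monthly glucose levels are scheduled, but that is not a record of episodes between visits.

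**Conclusion.** The concern holds as a dropped declared outcome. Both components of the protocol's only named safety outcome are absent by name from SAP 9 and absent from Table 10. Two of SAP 9's own three specific parameters are missing from that table as well. The consequence is that zero events, unrecorded events and omitted events cannot be told apart, so no conclusion on the declared outcome can be drawn from what is shown.

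This rests on reading item 4 as one outcome with two parts, and on Table 10 being the full safety table. It is legible, with arm sizes, seven rows and a footnote. The conclusion does not depend on any event rate, and it does not say that the data are unavailable or that events were withheld.

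**What to change.** Reconcile Protocol Outcomes item 4, SAP 9 and Table 10:

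1. Name hypoglycemia and serious adverse events as safety outcomes in SAP 9. State how each was defined and how it was captured.
2. For hypoglycemia, report by arm the patients with at least one episode and the number of episodes. Use Fisher's exact test for patient counts only, and a count or rank comparison such as Mann-Whitney for episodes per patient.
3. For serious adverse events, report by arm the patients with at least one event.
4. Give exact 95% confidence intervals for the risk differences in patient proportions.
5. Add these rows to Table 10, printing zeros where none occurred, and either report hypotension and electrolyte imbalance there or say where they are reported.
6. Mark definitions and rows added now as post hoc. The SAP is dated 11/3/2024 and gives November 2023 as the end of the study.
7. If episodes or serious events were not recorded, say so and draw no conclusion on that outcome.

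Rates per patient-month and a split by diabetes status are optional. The former needs exposure time, which the documents do not give.

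The cost is a few sentences in the SAP, a few table rows and a review of existing records. The documents do not show how complete those records are for episodes between visits, so step 7 may apply.
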